3.2.2. Criteria for Dose Escalation

The study has been designed to establish the MTD defined as the dose that yields approximately 27.5% probability of DLT and considers equivalent doses that yield probability of DLT in the interval (Equivalence Interval) 22.5% to 32.5%.

Typically patients will be enrolled in cohorts of 2 to 4, but patients could be initially enrolled in cohorts of 1-2 for the lower doses (see section [Dose Escalation Phase \(Part 1\)](#)). The initial 2-4 patients to be included in a cohort will be open to any of the tumor types outlined in [Appendix 2](#). When required to expand a cohort for further evaluation of the MTD, enrollment of patients may be limited to those with NSCLC, SCCHN, CRC or TNBC.

For IV administration cohorts, initial dose levels are provided in [Table 1](#) and will be followed if no DLTs are observed; intermediate doses may be evaluated based on clinical findings. Subsequent maximum dose increases will be a maximum of 2-fold (100%) if no DLTs are observed. For SC administration cohorts, during the initial dose escalation levels, maximum dose increases will be up to 3-fold if no DLTs or safety events that are approaching the limit of tolerability are observed. The initial dose to be evaluated for SC administration will be equal to the dose level selected as the IV Dose Prime. The evaluation of the IV and SC routes of administration will proceed through dose escalation independently according to the mTPI method. Once the first DLT is observed, the maximum increase would follow a modified Fibonacci series in case of dose escalation (ie, 67%, 50%, 33%, etc.). Patients will be assigned to a dose that is closest to the current MTD prediction based on the mTPI method. The mTPI method relies upon a statistical probability algorithm, calculated using all patients treated in prior and current cohorts at the same dose level to determine (Decision Rules) where future cohorts should involve dose escalation, no change in dose, or dose de-escalation as presented in [Table 2](#) (see also Section [Statistical Methods and Properties](#)).

Table 1. Dose Escalation Levels for IV Administration

Dose Level	Dose (ng/kg)
1 (Starting Dose)	1.5
2	7.5
3	20
4	50
5	100
6	200
7	300
8	400

* Intermediate doses may be evaluated based on clinical findings (eg, a dose between 20 and 50 ng/kg).

Table 2. Decision Rules

Number of Patients Having DLT	Number of Patient Treated at a Dose Level										
	n=2	n=3	n=4	n=5	n=6	n=7	n=8	n=9	n=10	n=11	n=12
0	E	E	E	E	E	E	E	E	E	E	E
1	S	S	S	S	E	E	E	E	E	E	E
2	U	D	S	S	S	S	S	S	E	E	E
3		U	U	D	D	S	S	S	S	S	S
4			U	U	U	U	D	D	D	S	S
5				U	U	U	U	D	D	D	D
6					U	U	U	U	U	U	U
7						U	U	U	U	U	U

D: De-escalate the dose; E: Escalate the dose; S: Stay at the dose; U: Unacceptable toxicity

Note: If one patient has a DLT event observed in a dose cohort with 1 patient enrolled, additional patients (eg, 1 or 2) may be enrolled for dose escalation assessment.

Dose escalation will stop under any of the following conditions:

- The maximum sample size has been achieved;
- 6-12 patients have been enrolled at a dose that is predicted to be the MTD;
- All doses explored appear to be overly toxic and the MTD cannot be determined.

Intrapatient dose escalation, other than the potential inclusion of priming doses, will not be permitted in this study.

3.3. DLT Definition

Severity of adverse events will be graded according to CTCAE version 4.03 ([Appendix 6](#)). For the purpose of dose escalation, any of the following adverse events occurring in the first cycle of treatment (21 days after the first dose) will be classified as DLTs, unless there is a clear alternative explanation (eg, related to underlying disease/progression):

Hematologic:

- Grade 4 neutropenia lasting ≥ 5 days;
- Febrile neutropenia defined as an absolute neutrophil count (ANC) $<1.0 \times 10^9/L$ with a single temperature of $>38.3^{\circ}\text{C}$, or 101°F , or a sustained temperature of $\geq 38^{\circ}\text{C}$, or 100.4°F , for more than one hour;
- Grade ≥ 3 neutropenia with infection;
- Grade 3 thrombocytopenia with Grade ≥ 2 bleeding;

- Grade 4 thrombocytopenia.

Non-hematologic:

- Grade 4 toxicities (not attributed to CRS) that are considered clinically significant;
- Grade 3 toxicities (not attributed to CRS) that are considered clinically significant despite maximal supportive care (eg, nausea, vomiting, diarrhea, easily corrected electrolyte abnormalities) that last >72 hours;
- Grade ≥ 3 CRS considered not to be due to an IRR, allergic reaction or anaphylaxis, except those i) not maximally treated or ii) events that are maximally treated, (eg, including the use of tocilizumab and/or vasopressors), and resolve to \leq Grade 2 within 72 hours;
- Delay by more than 2 weeks in receiving the next scheduled dose due to persisting treatment related toxicities.

In addition, clinically important or persistent toxicities that are not included in the above criteria may be considered a DLT following review by the sponsor and the investigators.

Grade 3 infusion reaction, allergic reaction or anaphylaxis will not be considered as DLTs but may be a reason for study discontinuation and should be reviewed with the sponsor.

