3.2.1. Evaluation of a Priming Dose

Based on toxicity study results, the evaluation of a priming dose to allow subsequent higher level dose administration may be instituted in this study. In addition, blinatumomab, an approved bispecific agent for the treatment of ALL, has been able to overcome symptoms of cytokine release syndrome (CRS) with the implementation of a priming dose (Topp et al, 2014).²¹ Therefore, this study may implement the evaluation of a priming dose during the escalation phase.

The initial priming dose will be defined to facilitate subsequent dose escalation towards establishing the MTD of a dosing regimen that includes a priming dose. The study aims to determine a MTD for an IV dose regimen that does not include a priming dose, and an independent MTD for an IV dose regimen that includes a priming dose. In addition, the study aims to similarly determine a MTD for PF-06671008 administered subcutaneously that may or may not include a priming dose.

The decision to evaluate a regimen that includes a priming dose may be made by the investigators and sponsor prior to reaching a MTD using the following criteria as guidance:

If a dose level induces symptoms consistent with Grade 3 CRS as defined in [Appendix 8](#) lasting for >24 hours considered not to be due to an infusion related reaction (IRR), allergic reaction, anaphylaxis or other causes in a cohort of 2-4 patients after the initial infusion, an additional 1-4 patients (up to approximately 6 patients overall) will be enrolled at that dose to confirm implementation of a priming dose (Dose Prime) for subsequent cohorts. If an additional confirmed CRS of Grade 3 lasting for >24 hours is observed at that dose, then a lower dose, which has been evaluated in at least 2-4 patients, will be chosen as a priming dose (Dose Prime) for subsequent cohorts. If a Dose Prime is selected, dose escalation will continue to determine the MTD of a dose regimen that includes a priming dose. The evaluation of a Dose Prime may be implemented for both the IV and/or SC routes of administration.

If a dose level induces confirmed CRS of Grade 4 considered not to be due to an IRR, allergic reaction, anaphylaxis or other causes, then a lower dose, which has been evaluated in at least 2-4 patients, will be chosen as a priming dose (Dose Prime) for subsequent cohorts.

[figure not shown]

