Cytokine Release Syndrome	
 Grade 2: Hold PF-06671008 until resolved and resume at same dose level. If Grade 2 CRS reoccurs, hold PF-06671008 until resolved and consider reduction by 1 dose level based on the investigator's discretion. Grade 3: Hold PF-06671008 until resolved and consider reduction by 1 dose level based on the investigator's discretion. If Grade 3 CRS recurs despite reduction, permanently discontinue PF-06671008. Grade 4: Permanently discontinue PF-06671008.
Hematologic toxicity considered related to PF-06671008 per investigator judgment 
 Grade 4 neutropenia, ie, ANC <500 mm³ (1.0 x 10⁹/L) for more than 5 days or Febrile neutropenia, ie, fever >38.3°C (101°F) or a sustained temperature of ≥38°C (100.4°F) with ANC <1000/mm³ or Grade ≥3 neutropenic infection or Grade 4 Thrombocytopenia, ie, PLTS <25,000 mm³ (25.0 x 10⁹/L) or Grade 3 Thrombocytopenia, ie, PLTS <50,000 mm³ (50.0 x 10⁹/L) with bleeding. 	
 Hold PF-06671008 until recovery of ANC to ≥1.0 x 10⁹/L (1,000 cells/mm³) and platelets ≥75 x 10⁹/L (75,000 cells/mm³). Reduce PF-06671008 by 1 dose level. If toxicity reoccurs (grades as described on the left side) despite dose reduction, patients may either be held until recovery and continuation at same dose, or undergo further dose reduction by 1 more dose level (except for the first cohort).
Other grade 4 hematologic toxicity considered related to PF-06671008 per investigator judgment	
 Hold PF-06671008 until recovery to Grade 0-1 or baseline and reduce PF-06671008 dose by 1 dose level. If toxicity reoccurs (Grade 4) despite dose reduction, patient may either be held until recovery and continuation at same dose, or undergo further dose reduction by 1 more dose level.
No recovery of toxicities within 4 weeks of scheduled PF-06671008 infusion	
 Discontinue treatment, unless restarting treatment at reduced dose level is in the patient's best interest per investigator judgment and after consultation with Pfizer's medical monitor (eg, clear clinical benefit and no alternative treatment options).

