4	6	0.470	0.266	0.260	0.004	12.333	3.334	0.270
4	9	0.504	0.263	0.228	0.005	16.235	4.469	0.275
4	12	0.560	0.189	0.245	0.006	21.146	6.033	0.285
5	6	0.676	0.000	0.221	0.103	8.496	3.193	0.376
5	9	0.656	0.000	0.178	0.166	11.459	4.322	0.377
5	12	0.616	0.000	0.176	0.208	14.765	5.531	0.375

Appendix 8. Suggested Cytokine Release Syndrome Management Algorithm and Revised CRS Grading System

Adapted from D.W.Lee, et al: *Current Concepts in the Diagnosis and Management of Cytokine Release Syndrome*. *Blood* 124 (2014) 188-195.

Suggested tocilizumab administration: 4 mg/kg over 1 hour; consider a second dose if no clinical improvement within 24 to 48 hours.

CRS Revised Grading System

Grade	Toxicity
1	Symptoms are not life threatening and require symptomatic treatment only, eg, fever, nausea, fatigue, headache, myalgias, malaise
2	Grade 2 hypoxia* [decreased oxygen saturation with activity (eg, pulse oximeter <88%); intermittent supplemental oxygen] or Hypotension responsive to fluids or low dose of one vasopressor or Grade 2 organ toxicity
3	Grade 3 hypoxia* [decreased oxygen saturation at rest (eg, pulse oximeter <88% or partial pressure of oxygen (PaO ₂) <=55 mm Hg)] or Hypotension requiring high dose or multiple vasopressors or Grade 3 organ toxicity or grade 4 transaminitis
4	Life-threatening symptoms Grade 4 hypoxia* [life-threatening airway compromise; urgent intervention indicated (eg, tracheotomy or intubation)] Grade 4 organ toxicity (excluding transaminitis)
5	Death

*Modification to the Lee et al CRS Revised Grading System according to the CTCAE v4.03. Transient decreases in oxygen levels below 88% will not be considered to have met the criteria.

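### The CRS exceptions in the DLT definition have no grade ceiling, so a Grade 4 CRS can be counted as a non-DLT

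*Protocol*

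**What the plan says.** **DLT rule for CRS (Protocol 3.3).** CRS of Grade 3 or higher that is not explained by an infusion reaction, allergy or anaphylaxis is a DLT, "except those i) not maximally treated or ii) events that are maximally treated" and that come down to Grade 2 or below inside 72 hours. The rule sets a lowest grade but no highest grade.

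**Other criteria in 3.3.** The general Grade 4 criterion reads "Grade 4 toxicities (not attributed to CRS) that are considered clinically significant", and the general Grade 3 criterion has the same carve-out. A further criterion covers a dose delay of more than two weeks caused by toxicity that persists. A closing clause says that "clinically important or persistent toxicities that are not included in the above criteria may be considered a DLT" after sponsor and investigator review. A separate sentence says that "Grade 3 infusion reaction, allergic reaction or anaphylaxis will not be considered as DLTs".

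**Handling of Grade 4 CRS elsewhere.**
- Appendix 8 classes Grade 4 as life-threatening and gives as one form "life-threatening airway compromise; urgent intervention indicated (eg, tracheotomy or intubation".
- Table 3 (Protocol 5.4.8) says "Grade 4: Permanently discontinue PF-06671008". For Grade 3 it says to hold treatment and consider a reduction.
- Protocol 3.2.1 provides that "If a dose level induces confirmed CRS of Grade 4 considered not to be due to an IRR" or another listed cause, a lower tested dose becomes the priming dose for later cohorts. A Grade 3 event must last more than 24 hours and be followed by a further confirmed event. The decision to prime "may be made by the investigators and sponsor prior to reaching a MTD using the following criteria as guidance".

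**The concern.** Table 3 and 3.2.1 both treat Grade 4 CRS as a different class of event from Grade 3. The exceptions in 3.3 do not make that distinction. A patient could be intubated for CRS, recover within 72 hours, be permanently taken off the drug, and still enter the dose-finding data as DLT-free.

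DLT is the Part 1 primary endpoint. It determines the Table 2 decisions and the MTD rule in 3.4. CRS is also the toxicity around which the priming strategy, the inpatient stays and the 72-hour stagger are built. A gap in counting its most severe grades therefore affects the toxicity that matters most for choosing the dose.

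**Working it through.** **Step 1. Which criterion catches a Grade 4 CRS that resolves in 72 hours?** Assume the event meets none of the hematologic criteria.

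| Criterion in 3.3 | Applies? |
|---|---|
| CRS of Grade 3 or higher | No: exempt under (ii) if maximally treated, under (i) if not |
| General Grade 4 and Grade 3 criteria | No: both exclude CRS |
| Delay of more than two weeks | No: needs persisting toxicity, and Table 3 has already ended dosing |
| Closing clause | Only if the sponsor and investigators choose to use it |

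Exception (i) is the wider one. On its plain wording it has no time or resolution condition, so it also reaches prolonged Grade 4 CRS and, literally, Grade 5.

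**Step 2. Does the patient stay in the count?** Protocol 9.1 and SAP 4.3 remove patients only for major treatment deviations in Cycle 1. Nothing listed there covers stopping for CRS. SAP 6.2.1 summarizes DLTs in this same per-protocol set, so the patient is in the denominator and not in the numerator.

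**Step 3. Effect on Table 2** (events exempt, no other DLTs).

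| Patients | Exempt events | Decision as counted | Decision if counted as DLTs |
|---|---|---|---|
| 2 | 1 | E | S |
| 2 | 2 | E | U |
| 3 | 1 | E | S |
| 3 | 2 | E | D |

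These are Table 2 readings only. The priming guidance in 3.2.1 runs alongside and may redirect the next cohort.

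**Step 4. Effect on the MTD rule.** Section 3.4 requires an observed DLT rate x/n of at most 0.325 in 6 to 12 evaluable patients. The table gives the largest qualifying x and the next value.

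| n | Largest x | x/n | (x+1)/n |
|---|---|---|---|
| 6 | 1 | 0.167 | 0.333 |
| 7 | 2 | 0.286 | 0.429 |
| 8 | 2 | 0.250 | 0.375 |
| 9 | 2 | 0.222 | 0.333 |
| 10 | 3 | 0.300 | 0.400 |
| 11 | 3 | 0.273 | 0.364 |
| 12 | 3 | 0.250 | 0.333 |

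In every row the last column exceeds 0.325. At the limit, one exempted event keeps a dose eligible that would otherwise fail.

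**Step 5. The plan's escalation probabilities, as context.** Protocol 9.2 assumes escalation on 0/3 or 1/6. With true DLT rate p, P = (1−p)³ + 3p(1−p)²·(1−p)³. For p = 0.1 this is 0.729 + 0.177 = 0.906 (stated 0.91). For p = 0.3 it is 0.343 + 0.151 = 0.494 (stated 0.49). All nine stated values reproduce.

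Purely as an illustration, assume other DLTs at 10%, Grade 4 CRS at 10%, 20% or 30%, and no priming step. P is then 0.71, 0.49 or 0.31 if all Grade 4 CRS is counted; 0.81, 0.71 or 0.60 if half is exempt; and 0.91 throughout if all is exempt. None of these rates comes from the documents.

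**The case against.** The strongest reply is that the CRS rule is deliberate. Both general criteria carve CRS out, a dedicated criterion sets its own terms, and priming is the intended response to CRS. Whether reversible, treated CRS should limit the dose is a clinical judgement. That defends exempting brief Grade 3 events, and the fix keeps that exemption. It does not explain why the DLT count should ignore the Grade 3/Grade 4 line that Table 3 and 3.2.1 both draw.

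Several other points do stand:

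- **No contradiction.** A reader might infer that 3.3 contradicts Table 3 and 3.2.1. It does not. Table 3 governs one patient's dosing, 3.2.1 the regimen of later cohorts, and 3.3 the count. All can be followed together; the severity handling is inconsistent.
- **The infusion-reaction sentence is weak support.** It names Grade 3 only, but it concerns another class of event and could be a deliberately different rule.
- **Escalation is not automatic.** A reader might take Step 3 to mean that the next cohort gets a higher unprimed first dose. If the 3.2.1 guidance is followed after a first-dose Grade 4 event, it does not. Section 9.7 adds ongoing review of events at each dose level, and initial patients are staggered by 72 hours. These safeguards are guidance, discretion or procedure, and they leave the count unchanged.
- **The Grade 5 reading is literal and presumably unintended.** It needs a fatal case to be judged not maximally treated and the closing clause to go unused. The Appendix 8 management algorithm is a figure that could not be read in the available text, so what maximal treatment means cannot be fully judged.
- **The boundary arithmetic is generic.** Any single reclassified DLT would act the same way at the limit.

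**Conclusion.** The point holds as a gap in a stated rule. By its listed criteria, 3.3 lets Grade 4 CRS count as a non-DLT, and only a discretionary clause can reverse that. The priming guidance and safety review reduce the risk to later cohorts. They do not repair the count at the dose where the event occurred, although 3.4 still seeks an MTD for the unprimed IV regimen from that count.

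The size is conditional. At the 0.325 limit one uncounted event decides eligibility for every n from 6 to 12; away from the limit it may change nothing. A reader might infer from Step 5 that the chance of escalating rises from 0.49 to 0.91. The documents do not support that as an estimate, because they give no Grade 4 CRS rate and no share that would be exempt, and the calculation omits priming. No size of bias is claimed. The conclusion rests on the plain wording of 3.3 and on the closing clause remaining optional.

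**What to change.** In Protocol 3.3, limit both CRS exceptions to Grade 3. State that any Grade 4 or 5 CRS not attributed to an infusion reaction, allergy or anaphylaxis is a DLT, whatever its treatment or duration. The existing allowance for Grade 3 events can stay as it is.

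This is a wording change in one criterion. Its cost is a possibly more conservative MTD if brief Grade 4 CRS occurs. No extra display is needed: the gap concerns Grade 4 and above, DLTs are already listed by dose level (Protocol 9.6.1), and adverse events are already summarized by worst grade, dose and cycle (SAP 6.2.2).

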3. STUDY DESIGN

3.1. Study Overview

This is a Phase 1, open-label, multi-center, multiple-dose, safety, PK CCI study of single-agent PF-06671008. This study contains two parts, dose escalation (Part 1) followed by dose expansion (Part 2). Sequential cohorts of patients with tumor types with the potential to have P-cadherin expression (see [Appendix 2](#)), that are resistant to standard therapy or for whom no standard therapy is available, will receive escalating doses of PF-06671008 in Part 1 of the study. In addition, at clinically relevant dose levels of 100 ng/kg or higher (ie, doses where the exposure is near the target effective exposure) where the safety is confirmed in the initial 2-4 patients dosed, approximately up to 5 additional patients with CRC, TNBC, NSCLC or squamous cell carcinoma of the head and neck (SCCHN) may be enrolled. CCI

A large rectangular black box redacting several paragraphs of text.

Up to approximately 152 patients are expected to be enrolled in the study overall. The actual number of patients enrolled will depend on the tolerability of PF-06671008 and the number of dose levels required to identify the MTD.

PF-06671008 will be administered as a weekly IV infusion in 21-day cycles with a starting dose of 1.5 ng/kg. There will be a minimum 72-hour interval between the first dose administered to each of the initial patients (ie, patients contributing to initial DLT evaluation) enrolled at a new dose level due to the unknown time course of possible infusion-related reaction or cytokine release. All patients will be observed in-patient for at least 24 hours after the first dose on C1D1. At doses of 100 ng/kg or higher, especially when the total dose

[figure not shown]
A small rectangular black box redacting several lines of text.

exceeds 10,000 ng, additional in-patient overnight observation for subsequent doses beyond C1D1 may be considered based on the investigator's discretion and should be discussed with Pfizer.

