In addition, PF-06671008 will also be administered in cohorts as a weekly SC injection in 21-day cycles with a starting dose equal to the dose level selected as the IV Dose Prime (See Section [Evaluation of a Priming Dose](#)). Dose escalation cohorts with PF-06671008 SC administration will be evaluated independently in parallel with dose escalation cohorts evaluating PF-06671008 IV administration (See Section [Criteria for Dose Escalation](#)). For cohorts where a SC route of administration will be evaluated, there will also be a minimum 72-hour interval between the first dose administered to each of the initial patients (ie, patients contributing to initial DLT evaluation) enrolled at a new dose level due to the unknown time course of possible cytokine release. All patients who will be dosed subcutaneously will be observed in-patient for at least 48 hours after the first dose on Cycle 1 Day 1 (C1D1). Additional in-patient observation for subsequent cycles beyond C1D1 may be considered based on the investigator's discretion and should be discussed with Pfizer. Evaluation of either the IV or SC route of administration may be discontinued based on emerging clinical and safety data.

In the event study treatment administration is delayed due to toxicities during Cycle 1, the day when the patient receives their 4th dose of study drug will be counted as Day 1 of Cycle 2.

Treatment with investigational product will continue until either disease progression, patient refusal, or unacceptable toxicity occurs, whichever is earliest, unless the investigator and medical monitor agree to treatment beyond disease progression based on individual benefit/risk assessments.

Figure 3. Overall Study Design

The proposed doses, schedule(s), and PK time points may be reconsidered and amended during the study based on the emerging safety and PK data.

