In addition, observation of a confirmed CRS event that meets the above qualifications following later infusions (ie, after Cycle 1 Day 1) or CRS events that are approaching the limit of tolerability may prompt the investigators and sponsor to include evaluation of a Dose Prime for subsequent cohorts.

After confirmation of the safety of Dose Prime, the treatment schedule will implement the inclusion of the fixed priming dose as the first dose (C1D1) followed by a second dose (C1D8) that will continue to be escalated in subsequent cohorts following an mTPI method in cohorts of 2-4 patients. After the MTD has been established, the priming dose may potentially be further verified in connection to the established MTD/RP2D, including consideration of more than one priming step, if indicated, using information from all patients who were included in the initial priming dose determination as well as those enrolled in subsequent dosing cohorts.

The primary DLT observation period for cohorts that include Dose Prime will be 21 days following the first dose (C1D1). The dose escalation should a Dose Prime be instituted is depicted in Figure 4.

For cohorts instituting a Dose Prime, there will be a 72 hour observation period between the first dose administered to each of the initial patients enrolled (ie, patients contributing to initial DLT evaluation) at a new dose level. In addition to in-patient observation following the C1D1 dose, patients enrolled in cohorts instituting a Dose Prime must also undergo in-patient observation for at least 24 hours (for cohorts where PF-06671008 will be administered IV) or 48 hours (for cohorts where PF-06671008 will be administered SC) following the C1D8 dose.

Figure 4. Study Schematic Should Dose Prime Be Explored

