5.4.7. Dose Delays

Re-treatment following treatment interruption for treatment-related toxicity or at the start of any new cycle may not occur until all of the following parameters have been met:

- ANC $\geq 1,000/\text{mm}^3$.
- Platelets count $\geq 50,000/\text{mm}^3$.
- Non-hematologic toxicities have returned to baseline or Grade ≤ 1 severity (or, at the investigator discretion, Grade ≤ 2 if not considered a safety risk for the patient).

If a treatment delay results from worsening of hematologic or biochemical parameters, the frequency of relevant blood tests should be increased as clinically indicated.

If these conditions are met within 14 days of treatment interruption or cycle delay, PF-06671008 may be resumed. Refer to Section Dose Reductions for AEs requiring dose reduction at the time of treatment resumption.

If treatment interruption due to toxicity exceeds 14 days, treatment with this agent should be permanently discontinued.

The day when the patient receives their 4th dose of study drug will be counted as Day 1 of the next cycle. Subsequent cycles will be 21 days in length regardless of treatment delays.

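### The DLT criterion of a dose delay beyond 2 weeks is first met after the 21-day DLT window, and no text stops a patient on hold at Day 21 from being counted as DLT-free

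*Protocol*

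**What the plan says.** Protocol section 3.3 applies to events "occurring in the first cycle of treatment (21 days after the first dose) will be classified as DLTs". Among the non-hematologic criteria it lists "Delay by more than 2 weeks in receiving the next scheduled dose due to persisting treatment related toxicities". It closes with a discretionary clause, under which "persistent toxicities that are not included in the above criteria may be considered a DLT following review by the sponsor and the investigators".

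The schedules of activities give a dose every 7 days by either route, so Cycle 1 doses fall on Days 1, 8 and 15 and C2D1 on Day 22. Sections 3.2 and 3.2.1 set the primary DLT observation period at 21 days from C1D1, with or without a priming dose. SAP sections 2.2.1 and 2.2.2 repeat this. In priming cohorts the fixed first dose is "followed by a second dose (C1D8) that will continue to be escalated in subsequent cohorts".

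Section 3.1 gives Cycle 1 a different end when toxicity delays dosing: "the day when the patient receives their 4th dose of study drug will be counted as Day 1 of Cycle 2". Section 5.4.7 adds: "If treatment interruption due to toxicity exceeds 14 days, treatment with this agent should be permanently discontinued".

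Cohort decisions come from Table 2 and Appendix 7, which use the number of DLTs and the number of patients treated at the dose. Neither says how to enter a patient whose dose is on hold when the 21 days end. Sections 9.1 and 9.2 and SAP section 6.2.1 do not say either.

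**The concern.** A first-cycle DLT is the primary endpoint of Part 1 and the only toxicity input to the mTPI table. A listed criterion that is met only after the window closes can be missed when the escalation decision is made.

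The other criteria leave a gap that this one is there to fill. Several toxicities can keep a patient off drug under sections 5.4.6 to 5.4.8 without being another listed DLT:

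- platelets from 25,000 to below 50,000 without Grade 2 or higher bleeding;
- ANC of 500 to 999 without fever or infection;
- intolerable Grade 2 non-hematologic toxicity;
- CRS of Grade 3 that was not maximally treated, or that fell to Grade 2 within 72 hours on maximal treatment. Table 3 holds dosing for Grade 2 and Grade 3 CRS until it resolves.

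Such a patient stays evaluable under section 9.1, which asks only for one dose and no major treatment deviation. At stake is a next cohort that starts at a higher dose while a patient at the current dose is still off treatment for toxicity. Section 3.2.2 also makes the maximum step smaller once a first DLT has been observed, so a first DLT recognised late can affect the step size as well.

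**Working it through.** **1. The plan's nearest computed figure.** No sample size rests on this point. Section 9.2 tabulates the probability of escalating when 0/3 or 1/6 patients have a DLT, which is (1−p)³ + 3p(1−p)² × (1−p)³. At p = 0.30 this is 0.343 + 0.151 = 0.494, against 0.49 stated. All nine tabulated values reproduce.

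**2. First day on which the criterion is met.** For a dose due on Day s, a delay of exactly 14 days is Day s + 14, and the first day beyond 14 days is Day s + 15.

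| Dose held | Due | First day >14 days late | Days late at Day 21 |
|---|---|---|---|
| Second | Day 8 | 8 + 15 = Day 23 | 13 |
| Third | Day 15 | 15 + 15 = Day 30 | 6 |
| C2D1 | Day 22 | 22 + 15 = Day 37 | not yet due |

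If the window is taken to end on Day 22 (Day 1 + 21), the first two delays are 14 and 7 days, and neither is more than 14. With the ±1 day visit window the first two dates become Days 22–24 and 29–31. The only overlap is a second dose counted as due on Day 7 together with a window ending on Day 22.

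**3. Priming cohorts.** The escalated dose is first given on Day 8. The next dose that its toxicity can delay is Day 15, so Day 30 is the earliest date for a hold that it causes.

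**4. The 4th-dose rule.** Assume that held doses are postponed, not skipped. After a 14-day hold of the Day 8 dose, doses 2, 3 and 4 fall on Days 22, 29 and 36. After a 14-day hold of the Day 15 dose, doses 3 and 4 fall on Days 29 and 36. Cycle 1 then runs to Day 35 under section 3.1 but 21 days under section 3.3. The text does not say which governs for DLTs.

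**5. How many patients can be open at once.** Section 3.1 sets the spacing: "There will be a minimum 72-hour interval between the first dose administered to each of the initial patients". Take that minimum, and a decision on the last patient's Day 21. Earlier patients are then at Days 24, 27 and 30. A Day 8 hold (resolved by Day 23) is still open only in the last patient. A Day 15 hold (resolved by Day 30) can be open in up to 3. Wider spacing or a later decision lowers both counts.

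**6. Effect in Table 2.** With 0 DLTs the entry is Escalate at every n from 2 to 12. With 1 DLT it is Stay at n=2, 3, 4 and 5 and Escalate from n=6. With 2 DLTs in place of 1, Stay becomes Unacceptable at n=2 and De-escalate at n=3, and Escalate becomes Stay at n=6 to 9.

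**7. Illustration only.** The documents give no share of DLTs that would be identified by delay alone. Assume a true DLT rate of 30% and a share f unseen at every decision, so that the visible rate is 0.30(1−f). For f = 10%, 20% and 30% the visible rate is 0.27, 0.24 and 0.21, and the formula in step 1 gives 0.56, 0.62 and 0.69 against 0.49. These are upper values, because by the second decision a hold in the first three patients would usually have declared itself.

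**The case against.** The best reply is that section 3.3 limits when the adverse event occurs. The event is the toxicity, and the delay is its consequence, so onset within 21 days is enough. The 4th-dose rule supports this, since a delayed patient is still in the first cycle. This stands as a workable reading. A reader might infer from the calendar that the criterion can never operate, and the documents do not support going that far. But on the onset reading the classification is known only after Day 21, so the question of how to enter the patient at Day 21 remains.

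The second reply is that people are watching. The closing clause of section 3.3 covers persistent toxicity, section 5.1 requires the sponsor's written permission before any patient is dosed, and section 9.7 provides ongoing discussion of events at each dose level. A careful team would probably wait. These controls are real, but they are discretionary and set no timing. They turn a listed DLT into an optional one in just the case for which it was listed.

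Third, a reader might infer that the patient is certainly withdrawn for toxicity on Day 23. Section 5.4.7 points to discontinuation once an interruption exceeds 14 days. Table 3, however, allows 4 weeks for recovery, with an exception after consultation with the medical monitor. Discontinuation at that date cannot be stated as fact.

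Fourth, no rule fixes the decision on the last patient's Day 21. Immediate opening of the next cohort appears only as a simulation assumption in Appendix 7. The count of up to 3 patients is therefore a limiting case.

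**Conclusion.** The point holds as a timing gap in a safety rule. On the nominal schedule the delay criterion is first met on Day 23, 30 or 37, after a window of 21 days. No readable text keeps a patient on hold at Day 21 from being entered in Table 2 as DLT-free. One DLT in place of none changes Escalate to Stay at n=2 to 5.

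The main exposure is a next cohort opened too early. A reader might infer a bias in the estimated MTD, but the documents do not show one. Table 2 pools all patients at a dose, a late DLT can be added to that count, and section 3.4 asks for 6 to 12 evaluable patients with a DLT rate of at most 0.325.

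The conclusion assumes weekly dosing on nominal days and a decision taken once 21 days have passed. It also assumes that the redacted parts of section 5.4 contain no waiting rule. The frequency of such holds is unknown. The change should be made because it concerns the primary endpoint of a first-in-patient escalation and costs little.

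**What to change.** Add to section 3.3:

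> A treatment-related toxicity with onset within 21 days of the first dose that delays the Day 8, Day 15 or C2D1 dose by more than 14 days is a DLT, even if the 14 days are exceeded after Day 21. A patient with a Day 8 or Day 15 dose on hold for such toxicity at Day 21 is not entered as DLT-free in Table 2 until dosing resumes or the hold exceeds 14 days. If a C2D1 hold later meets the criterion, the DLT is added to the count at that dose and Table 2 is re-read before further patients start at that dose or higher.

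C2D1 should be named because the present wording on the next scheduled dose already covers it. A rule limited to Days 8 and 15 would narrow the criterion.

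The cost is a conditional wait: at most 23 − 21 = 2 days for a Day 8 hold or 30 − 21 = 9 days for a Day 15 hold, and only when a patient is on hold at Day 21. A C2D1 hold causes no wait at Day 21. The SAP needs no change, because it does not restate the DLT criteria.
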